8.1.2. Assumption testing

No assumption testing will be performed.

8.1.3. Missing data handling

No imputation will be made for the missing values for the primary analysis, unless specified differently in the estimand strategy (see [Table 2-2](#), [Table 2-1](#)).

8.1.4. Subgroup analysis

Primary analysis will be replicated for the following subgroups:

- Age category (≥ 18 to < 40 , ≥ 40 years)
- Gender (Male, Female)
- Race (Not-White, White)
- Baseline body weight (< 70 , ≥ 70 kg)
- Baseline BMI (< 25 , ≥ 25 to < 30 , ≥ 30)
- Region (EE/ROW)
- Baseline ICS dose level (Medium, High)
- Age of asthma diagnosis (< 18 , ≥ 18 to < 40 , ≥ 40 years)
- Number of severe asthma exacerbation events within 1 year prior to the study (1, > 1)
- Number of controller medications at study entry (2, 3)
- Smoking history (Former, Never)
- Baseline FeNO (≥ 25 to < 50 , ≥ 50 ppb)
- Baseline Eosinophils (< 500 , ≥ 500 cells/ μ L)
- Baseline ACQ-5
 - (≤ 3 , > 3)
 - (≤ 3.5 , > 3.5)
- Baseline Global Lung Mucus Score
 - Low (0-3.5)
 - High (4-20)

Subgroups might be combined in case the sample size is too small.

In these subgroup analyses, nominal p-value will be provided for descriptive purpose only.

Results will also be illustrated with forest plots.

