9 STATISTICAL CONSIDERATIONS

9.1 STATISTICAL HYPOTHESES

For comparison of dupilumab treatment group to placebo, the following hypotheses of the 2 primary endpoints will be tested.

1. Null hypothesis: 1) the proportion of participants achieving response of FeNo <25 ppb at Week 24 is the same between dupilumab and placebo group; 2) the percentage change from baseline in untrimmed distal [s]iVaw is the same between dupilumab and placebo group.
2. Alternative hypothesis: 1) the proportion of participants achieving response of FeNo <25 ppb at Week 24 is different between dupilumab and placebo group; 2) the percentage change from baseline in untrimmed distal [s]iVaw is different between dupilumab and placebo group.

9.2 SAMPLE SIZE DETERMINATION AND PRESERVATION OF TYPE I ERROR FOR THE PRIMARY ENDPOINTS

To control the type-I error rate for the 2 primary endpoints, a hierarchical testing procedure will be applied at a 2-sided 5% significance level, ie, each hypothesis will be formally tested only if the preceding one is significant at 5% level. The hierarchy of the tests for primary endpoints will be:

1. Proportion of participants achieving response of FeNO <25 ppb at Week 24
2. Percentage change from baseline to Week 24 in untrimmed distal [s]iVaw at TLC

[REDACTED]

Assumptions for the [s]iVaw parameter were based on extrapolating the limited available data in asthma looking at associations between FEV₁ and lung imaging parameters. Clinically meaningful differences for the imaging parameters have not yet been established. However, expert opinion and literature suggest that they are more sensitive than the lung function parameters, such as pre-BD FEV₁ mentioned above. [REDACTED]

[REDACTED]

By replacing FEV₁ change from baseline at Week 24 with proportion of participants achieving response of FeNO <25 ppb at Week 24 as one of the primary endpoints, [REDACTED]

[REDACTED]

With the original assumptions for [s]iVaw, 87 evaluable participants will provide approximately 64% power with two-sample t-test at 2-sided 0.05 significance level.

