3. INVESTIGATIONAL PLAN

3.1. Overall study design and plan

This is a Phase IV, 2:1 randomized, parallel, multinational, multicenter study, with a 24-week double-blind placebo-controlled treatment period to assess the effect of dupilumab on airway inflammation through assessments of lung function, mucus plugging, and other lung imaging parameters in participants with asthma.

Approximately 97 participants will be randomly assigned to study intervention, in a 2:1 dupilumab to placebo ratio, such that approximately 87 evaluable participants complete the study, assuming a 10% dropout rate (approximately 58 in the active group and 29 in the placebo group). Randomization will be stratified by dose level (medium/high – no less than 40% in ‘high ICS’ stratum) of inhaled corticosteroids (ICS) and region (Eastern Europe (EE)/Rest of the World (ROW)). In total, no more than 40% participants should be in EE strata.

[figure not shown]
The study will comprise of:

- Screening period: 4 weeks (± 1 week), from signed informed consent to randomization (Day [-35, -21] to Day -1).
- Randomized, placebo-controlled treatment period: 24 weeks from baseline (Day 1).
- Post-treatment follow-up period: up to 12 weeks or until the participant switches to commercialized dupilumab (or other biologic product), whichever comes first.

Study duration for each participant will be a total of minimum 29 weeks and up to 41 weeks. A participant is considered to have completed the study if he/she has completed all phases of the study including the post treatment follow-up visit (V6).

The end of the study is defined as the date of the last visit of the last participant in the study.

Figure 3-1 Study plan

ACQ-7= 7-item Asthma Control Questionnaire; AQLQ(S) =Asthma Quality of Life Questionnaire with Standardized Activities; D=Day; FeNO= Fractional exhaled nitric oxide; FU= Follow-up; HRCT= High-resolution computed tomography; ICF=Informed Consent Form; mg=milligram; mL=milliliter; Q2W= every 2 weeks; R=Randomization; V=Visit

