8.1. Primary efficacy endpoint

The two primary endpoints are:

- Proportion of participants achieving response of FeNO <25 ppb at Week 24
- Percent change from baseline to week 24 in untrimmed distal specific airway volume ([s]iVaw) at total lung capacity (TLC) (see [Section 15.10](#))

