8.1.1. Primary analysis

Proportion of participants achieving FeNO <25 ppb at week 24 will be analyzed with a Cochran-Mantel-Haenszel (CMH) test adjusted by stratification factors (ICS dose level at baseline and region). Comparison of the proportions of responders between dupilumab and placebo will be derived, and corresponding odds ratios and 95% CI along with the p-value will be reported.

For participants who discontinued the study treatment not due to COVID-19 pandemic, off-treatment data will be used to determine the responder/non-responder status. For any participants who discontinued the study treatment due to COVID-19 pandemic, off-treatment data will be set to missing. Missing data at week 24 will be considered as non-responders.

Percent change from baseline in untrimmed distal [s]iVaw at TLC will be analyzed with a MMRM model under the MAR framework. The MMRM model will use percent change from baseline in untrimmed distal [s]iVaw up to week 24 as response variable and include study intervention (dupilumab, placebo), baseline value of untrimmed distal [s]iVaw at TLC, region (EE/ROW), ICS dose level (medium/high), visits (up to week 24), study intervention by visit interaction, and baseline untrimmed distal [s]iVaw at TLC by visit interaction terms all as fixed effects. An unstructured correlation matrix will be used to model the within-participant errors.

The Kenward-Roger approximation (ddfm=kr) will be used to estimate the denominator of degrees of freedom. Parameters will be estimated using restricted maximum likelihood method with the Newton-Raphson algorithm. The adjusted LS mean in percent change from baseline of each study intervention group, the LS mean difference between the dupilumab and placebo groups, and the corresponding SEs and 95% CIs will be provided at all scheduled visits. The p-value corresponding to the LS mean difference will be provided at Week 24 only.

For participants who discontinued the study intervention before Week 24 not due to the COVID-19 pandemic, off-study intervention imaging data measured up to Week 24 will be included in the analysis. In contrast, for any participants discontinuing the study intervention due to the COVID-19 pandemic, off-study intervention data will not be included (ie, set to missing) but will be assumed missing at random.

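### SAP 8.1.4 gives a p-value within each subgroup level but no estimate of whether the treatment effect differs between levels

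*SAP*

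**What the plan says.** SAP 8.1.4 introduces its list with "Primary analysis will be replicated for the following subgroups". It names 15 baseline factors. BMI and age at asthma diagnosis have three levels; the others have two. ACQ-5 is split once at 3 and again at 3.5.

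On reporting, the section says "In these subgroup analyses, nominal p-value will be provided for descriptive purpose only" and "Results will also be illustrated with forest plots". On small levels it says only "Subgroups might be combined in case the sample size is too small", with no minimum size.

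The analysis being repeated is in SAP 8.1.1: a stratified CMH test with odds ratio and 95% CI for FeNO <25 ppb, and an MMRM giving the LS mean difference with 95% CI for [s]iVaw. The interactions in the MMRM are "study intervention by visit interaction, and baseline untrimmed distal [s]iVaw at TLC by visit interaction terms all as fixed effects". None involves a subgroup factor. No other text in the public protocol or SAP adds a treatment-by-subgroup term, contrast or test.

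**The concern.** A p-value computed inside one level asks whether there is an effect in that level. It does not ask whether the effect differs from that in the other level. With about 29 evaluable placebo participants, a split often leaves one level below p=0.05 and the other above it even when the true effect is the same in both.

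At stake is how results by, for example, baseline FeNO, eosinophils, mucus score or region are read. Region matters most here. The protocol amendment history (10.12.1) says the region factor was changed because the earlier Phase 3 trial showed different dupilumab effects in Eastern Europe and elsewhere. The sponsor thus has a recorded reason to ask about effect modification by region, and the plan does not estimate it.

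**Working it through.** **Counts.** There are 15 factors. Counting both ACQ-5 cuts gives 16 partitions: 14 with two levels and 2 with three. Levels: 14 × 2 + 2 × 3 = 34. With two primary endpoints there are up to 34 × 2 = 68 within-level p-values, fewer if levels are merged.

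**Inputs.** Protocol 9.2: "With the original assumptions for [s]iVaw, 87 evaluable participants will provide approximately 64% power with two-sample t-test at 2-sided 0.05 significance level". SAP 3.1: about 58 evaluable on dupilumab and 29 on placebo, 10% dropout, at most 40% of participants in Eastern Europe. The [s]iVaw effect and SD and the FeNO response rates are redacted.

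**The plan's own figures.** The randomized number reproduces: 87 / 0.90 = 96.7, rounded up to 97. The 64% cannot be reproduced without the redacted inputs, so it was inverted. With a two-sample t-test, 58 vs 29, two-sided 0.05, the noncentrality is d × √(58 × 29 / 87) = 4.397d. Power of 64% requires d = 0.533 (0.527 by the normal approximation).

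**Power within a level for [s]iVaw** (same d, 2:1 kept inside each level, noncentral t):

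| Share of the 87 | Participants | Power |
|---|---|---|
| 60% | about 52 | 42.9% |
| 50% | about 44 | 36.7% |
| 40% | about 35 | 30.2% |
| 25% | about 22 | 20.0% |

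**Chance of discordant p-values with one common true effect.** With powers a and b in the two levels, this is a(1 − b) + b(1 − a).

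- 50/50: 2 × 0.367 × 0.633 = 46.5%.
- 40/60: 0.302 × 0.571 + 0.429 × 0.698 = 47.2%.
- Both levels significant: 13.5% (50/50) and 13.0% (40/60).

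A simulation of 40,000 trials per split (d = 0.532, level sizes varying at random) gave 46.7% and 47.4%. In it, a test of the difference between levels was significant in 5.1% and 5.2% of trials, and in only about 10% of the discordant pairs.

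**Sensitivity to d.** For equal halves with power p each, discordance is 2p(1 − p). This is at least 2 × 0.3 × 0.7 = 42% for any p from 30% to 70%, so a moderate error in the implied effect changes little.

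**FeNO, on assumed rates only.** Seven assumed pairs were tried, with placebo response 10-20% and dupilumab 40-60% (normal approximation for two proportions). Power in a half ranged from 48% to 85%. Discordance ranged from 25% to 50% at 50/50 and from 29% to 52% at 40/60. It is lower when the effect is large.

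**What an interaction test can do for [s]iVaw.** At 50/50, the standard error of the difference between the two level effects, in SD units, is √[2 × (1/29 + 1/14.5)] = 0.455. Power is about 22% for an interaction as large as the whole main effect (0.533) and 65% for one twice as large. If the tests were independent and unadjusted, the chance of at least one false interaction per endpoint would be 1 − 0.95^15 = 54%, or 56% with 16.

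**The case against.** The strongest reply is that the plan claims nothing from these p-values. They are labelled descriptive, no rule for subgroup claims exists, and the hierarchy in SAP 8.2.5 contains no subgroup. Level-specific estimates with 95% CIs and forest plots are already planned, so a reader can compare effects without using p-values. All of this stands. A reader might infer that subgroup effects are to be judged by significance, or that p-values are the only comparison on offer; the SAP supports neither.

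A reader might also infer that any subgroup differences seen will mostly be low power at work. That presumes equal true effects, and the regional difference recorded from the earlier trial means at least one factor could show a real one. Nor does 68 × 0.05 = 3.4 measure false effect modification: it assumes no effect anywhere.

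One might further suspect that the stratified CMH fails in small levels. The SAP allows merging, a stratum lacking one arm simply contributes nothing, and region or ICS is constant within its own subgroup and so drops out there.

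Finally, the replacement is weak too: about 22% power for a large interaction, and many unadjusted tests. For FeNO, if placebo response is 10-20% with 14 and 15 placebo participants in the two halves, the chance that at least one half has no placebo responder runs from 1 − (1 − 0.9^14)(1 − 0.9^15) = 39% down to 8%, so an ordinary logistic interaction may not be estimable. This is fair. It favours reporting an estimate with its interval over relying on a test, but it does not rescue the within-level p-values, which address a different question.

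**Conclusion.** The point holds as a minor one. SAP 8.1.4 reports 15 factors (16 partitions, 34 levels) without any estimate or test of a difference in effect between levels. For [s]iVaw, the planned p-values would disagree between two levels in about 46-47% of trials at a 50/50 or 40/60 split with no true difference, against a 5% false-positive rate for a direct test.

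The figure rests on an effect back-solved from the stated 64% power, an unadjusted t-test in place of the planned MMRM, 2:1 allocation within levels, and equal true effects. For FeNO the size is not established, because the rates are redacted. No primary or hierarchical conclusion is affected.

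**What to change.** In SAP 8.1.4, for each factor:

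- Keep the level-specific estimates, 95% CIs and forest plots, and add the treatment-by-subgroup interaction estimate with 95% CI and an exploratory p-value.
- For [s]iVaw, take the treatment-by-subgroup contrast at Week 24 from the MMRM fitted to the whole ITT set, with the subgroup terms and their interactions with treatment and visit added.
- For FeNO, report the ratio of odds ratios with a homogeneity-of-odds-ratio test, and use an exact or penalised method if a cell has no responders.
- Drop the within-level p-values.
- State that the interaction tests have low power and are not adjusted for multiplicity. A non-significant result does not show consistency, and an isolated significant one may be chance.

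The cost is SAP wording and a few extra model terms per factor, with no new data. The downside is the one to be stated in the SAP: many intervals will be wide and many results inconclusive.

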8.1.5. Sensitivity analysis

A sensitivity analysis on the two primary endpoints of achievement of FeNO <25 ppb at Week 24 and percent change from baseline to week 24 in untrimmed distal [s]iVaw at TLC will be carried out. For the latter, an analysis of covariance model (ANCOVA) with data from multiple imputation (MI) on missing results under an assumption of missing at random (MAR) will be used. For response of FeNO <25 ppb at week 24, a CMH testing procedure with data from multiple imputation (MI) on missing results under an assumption of missing at random (MAR) will be performed. Under this assumption, each missing score will be imputed 100 times and incorporated with non-missing data from 100 complete datasets. Each dataset will include FeNO / untrimmed distal [s]iVaw at baseline, week 4, week 12 (only for FeNO), and week 24, as well as relevant covariates specified below to support the analysis. Following steps will be conducted for this analysis. The number of imputations (100) will be informally verified by replicating sets of 100 imputations and checking whether the combined results are stable. If not stable, the number of imputations will be increased and informally checked as above, until stable estimates are obtained.

- Use the Markov chain Monte Carlo (MCMC) method to impute for intermittent missing values by study intervention group and to create 100 datasets with monotone missing pattern. According to the nature of the endpoint, minimum and maximum values will be specified in this imputation.
- For each of 100 datasets with monotone missing pattern created from MCMC imputation, use monotone regression method to impute remaining missing value by study intervention group up to week 24. In the imputation regression model, the following covariates will be included:
 - region (EE/ROW) and ICS dose level (medium/high)Percent change from baseline at week 24 and achievement of FeNO <25 ppb can be calculated with non-missing score or imputed score for every single participant in all datasets. All 100 datasets with full imputation for missing values will be input to the following models.
- Repeatedly perform ANCOVA modeling for each of 100 datasets with full imputation for missing values. Percent change from baseline of untrimmed distal [s]iVaw at TLC at week 24 will be analyzed on the ITT population in this ANCOVA model, and study intervention (Dupilumab, Placebo), baseline of the analyzed endpoint and respective above covariates, will be included as covariates.
- The adjusted LS means in change or percent change from baseline of each study intervention group, the LS mean difference between the dupilumab and placebo groups, and the corresponding SEs and 95% CIs of the differences generated from the 100 ANCOVA models will be combined using Rubin's formula and presented in a statistical table for the ITT population.

- Repeatedly perform CMH testing on each of 100 datasets with full imputation for missing values. Achievement of response of FeNO <25 ppb at week 24 will be analyzed on the ITT population, adjusted on stratification factors.
- The Wilson-Hilferty transformation will be used to perform a combined CMH test and odds-ratios will be combined using a log transformation and Rubin's formula. The combined p-value, odds-ratio and corresponding CIs will be presented in a statistical table for the ITT population.

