8.2.2. Fractional Exhaled Nitric Oxide (FeNO)

FeNO (see [Section 15.12](#)) will be summarized in terms of actual value and change from baseline at Week 24).

In addition, at each post-baseline visit, the change from baseline will be modelled using the same MMRM model as the one used for the secondary endpoint relating to pre-BD and post-BD FEV₁. LS mean of each study intervention group, LS mean difference between the dupilumab and placebo groups, and the corresponding SEs and 95% CIs will be provided at all scheduled visits. The p-value corresponding to the LS mean difference will be provided at Week 24 only. FeNO data may be logarithmically transformed prior to analysis if extreme skewness was observed based on blinded data review.

The same strategy as for MMRM model for primary endpoint untrimmed distal [s]iVaw will be used for the selection of the covariance structure if MMRM under unstructured correlation matrix fails to achieve convergence.

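### The multiple-imputation check on FeNO response should impute ln(FeNO): as written, it fits an unbounded regression to a positive, probably skewed measure and then cuts at 25 ppb

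*SAP*

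**What the plan says.** The primary analysis of FeNO response (SAP 8.1.1) counts a missing Week 24 value as non-response. SAP 8.1.5 then plans one missing-data check, multiple imputation under missing at random with 100 imputations:

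- **What is imputed.** The continuous score: "Each dataset will include FeNO / untrimmed distal [s]iVaw at baseline, week 4, week 12 (only for FeNO), and week 24".
- **Step 1, MCMC.** This fills intermittent gaps within arm. Here the SAP adds: "According to the nature of the endpoint, minimum and maximum values will be specified in this imputation".
- **Step 2, monotone regression.** For what remains, chiefly values lost to dropout, the plan is to "use monotone regression method to impute remaining missing value by study intervention group up to week 24", with region and ICS dose level as covariates. No bound, scale or transformation is given.
- **Classification.** Only then is response derived: "achievement of FeNO <25 ppb can be calculated with non-missing score or imputed score for every single participant in all datasets".

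SAP 15.12 says FeNO is reported in ppb. For the secondary FeNO change analysis, SAP 8.2.2 says: "FeNO data may be logarithmically transformed prior to analysis if extreme skewness was observed based on blinded data review". SAP 8.1.1 and Protocol 9.4.1 contain a similar optional clause. None of these is carried into 8.1.5.

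**The concern.** FeNO cannot be negative, and the SAP itself foresees that it may be skewed. A regression imputation draws from a symmetric, unbounded distribution around the fitted mean. Applied to ppb values, it can return FeNO below zero, and such a value counts as a response. It also gives the wrong probability of falling below 25 ppb, because both the centre and the lower tail of the fitted distribution are misplaced.

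Table 15-1 of the SAP lists this as the only sensitivity analysis for the endpoint tested first. Its purpose is to show whether the non-responder rule drives the result. A shift caused by the shape of the imputation model blurs that comparison for a reason unrelated to the missing data.

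**Working it through.** **1. How much has to be imputed.** SAP 3.1 gives 87 evaluable participants and 10% dropout: 87 / 0.90 = 96.7, which reproduces the planned 97. At 2:1 that is about 65 and 32 randomised against 58 and 29 evaluable, so about 7 and 3 values are missing.

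**2. Assumed inputs.** The public text gives no FeNO mean, SD or expected response rate, so these are assumptions:

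- baseline FeNO log-normal, underlying median 38 ppb, log-SD 0.6, truncated at the eligibility floor of 25 ppb (Protocol 5.1, I 06)
- follow-up SD parameter 0.4 or 0.6 on the log scale
- follow-up to baseline ratio 0.7, 0.9 or 1.0 on placebo and 0.35, 0.5 or 0.6 on dupilumab
- random dropout of 10% or 20%

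This makes 3 x 3 x 2 x 2 = 36 scenarios, each with 200 simulated trials and 6 imputations per trial. The monotone step was run by arm without bounds, once in ppb and once on the log scale, and then cut at 25 ppb.

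**3. Results.** Selected scenarios; treatment differences in response rate are in percentage points. NRI is the primary analysis's non-responder rule.

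| Missing | Ratio placebo / dupilumab, SD | Complete data | NRI | ppb MI | log MI | ppb minus log |
|---|---|---|---|---|---|---|
| 10% | 0.9 / 0.35, 0.4 | 64.9 | 58.8 | 64.7 | 64.9 | -0.25 |
| 10% | 0.9 / 0.5, 0.6 | 32.8 | 29.8 | 31.7 | 32.5 | -0.84 |
| 10% | 1.0 / 0.5, 0.6 | 39.4 | 35.5 | 37.8 | 39.2 | -1.34 |
| 20% | 0.7 / 0.35, 0.4 | 47.2 | 38.0 | 46.8 | 46.5 | +0.36 |
| 20% | 1.0 / 0.5, 0.6 | 38.7 | 30.8 | 35.8 | 38.0 | -2.19 |

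Over all 36 scenarios, ppb minus log ran from +0.2 to -1.3 points at 10% missing and from +0.4 to -2.2 at 20%. The ppb-scale difference was the smaller in 34 of 36. Against complete data, the third and fifth rows are 1.6 and 2.9 points low in ppb, but log imputation is also low there, by 0.2 and 0.7.

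A second set of 16 log-normal scenarios with the same baseline floor put the ppb-scale difference below the complete-data one every time: by 0.2 to 1.0 points at 10% missing and 0.3 to 2.2 at 20%. Log imputation was off by 0 to 0.2 and by up to 0.5.

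**4. Where the shift comes from.** Shift in the difference = missing fraction x (shift in imputed dupilumab rate - shift in imputed placebo rate).

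- Second row: imputed rates in ppb and log are 0.48 and 0.57 on dupilumab, 0.29 and 0.30 on placebo. 0.10 x [(0.48 - 0.57) - (0.29 - 0.30)] = 0.10 x (-0.08) = -0.8 points.
- Fifth row: 0.20 x [(0.51 - 0.61) - (0.26 - 0.25)] = 0.20 x (-0.11) = -2.2 points.

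Most of the shift is on dupilumab. With right skew the mean lies above the median, so a normal model centred on the mean puts too little below 25 ppb when the true response rate is about one half or more. On placebo the cut is lower in the distribution. There the misplaced centre and the heavy lower tail work against each other: the imputed rate was 0.20 in ppb against 0.17 on the log scale when the true rate was 0.145, but 0.35 against 0.39 when it was 0.380.

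**5. Negative values.** About 2% to 12% of imputed values in the 36 scenarios were negative. In the second row the shares were 0.084 on dupilumab and 0.107 on placebo. Even if none of these should have been responses, their net effect is 0.10 x (0.084 - 0.107) = -0.2 points, against a total of -0.8.

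**6. Scale of the effect.** With response rates near 0.6 and 0.2 in 65 and 32 participants, the standard error of the risk difference is sqrt(0.6 x 0.4 / 65 + 0.2 x 0.8 / 32) = 0.093. One point is about 0.1 standard error.

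**The case against.** - **The scale is not stated.** That imputation runs in ppb is an inference, and the plan has a blinded route to a log scale in SAP 8.1.1 and Protocol 9.4.1. This stands. However, the route is optional and depends on extreme skewness, and 8.1.5 does not mention it, so a programmer following 8.1.5 would use the reported unit. The bounds sentence could also be read as covering both steps. It sits in the MCMC bullet, and bounds would remove impossible values without correcting the shape.
- **The simulation favours its remedy.** Log-normal data suit log-normal imputation. This stands as a limit on the size. It does not rescue a model that permits negative FeNO.
- **Fewer values may be missing.** The early treatment discontinuation visit includes FeNO, participants are encouraged to continue to Week 24, off-treatment values are used unless the stop was due to COVID-19, and the Week 24 window opens at Day 127 with no upper limit (SAP 15.5). If less than 10% is missing, the effect shrinks in proportion.
- **The check still does its job.** In all 36 scenarios the ppb-scale difference remained larger than the non-responder one. This stands, and it is why the point is minor.

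A reader might infer that negative imputed values drive the shrinkage, or that the difference must shrink. Neither is supported: negative values arise in both arms and largely cancel, 2 of 36 scenarios went the other way, and the documents give no FeNO distribution from which to fix a direction.

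**Conclusion.** The gap is real and minor. As written, SAP 8.1.5 lets the monotone step impute negative FeNO and uses a poorly fitting model for a positive, probably skewed measure just before a threshold is applied. Under the assumed log-normal distributions, ppb-scale imputation usually understates the treatment difference by up to about 1 point at 10% missing and about 2 points at 20%, mainly by imputing too few dupilumab responders. Direction and size rest on those assumptions and on the ppb reading.

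Because FeNO response is tested first, a reader might infer that the confirmatory results are at risk. They are not. The hierarchy in SAP 8.2.5 follows the primary CMH test, which uses the non-responder rule; the sensitivity analysis enters neither the hierarchy nor the type I error.

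**What to change.** In SAP 8.1.5, state that FeNO at baseline and Weeks 4, 12 and 24 is transformed to ln(FeNO) before imputation, that both the MCMC and the monotone regression steps run on that scale, and that imputed values are back-transformed before classification as <25 ppb. Back-transformed values are always positive, so bounds for FeNO are no longer needed.

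The cost is one sentence in the SAP and one transform in the program. No data collection, sample size or primary analysis changes, and SAP section 1 places revisions to the planned analysis before database lock.
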